8.4. Analysis of the Primary Efficacy Endpoint

8.4.1. Primary Efficacy Analysis

The primary endpoint of the trial is the time from randomization to the first occurrence of any component of the clinical composite endpoint of nonfatal myocardial infarction, nonfatal ischemic stroke, cardiovascular death, and coronary revascularization.

Patients who do not have an event will be censored at withdrawal of consent, end of study, or death. The censor date will be the date of withdrawal of consent for follow-up, CSED or the subject's last assessment, or death, whichever comes first. The time to event/censoring in days will be derived as (Date of First Occurrence of Event/Censoring – Date of First Dose) +1. The primary analysis of the trial will use a likelihood ratio test based on a proportional hazards model stratified on sex, prior history of CVD, and statin use at baseline to test the null hypothesis of no association between assignment to active K-877 and the rate of the primary endpoint. All analyses will classify patients according to their randomized treatment assignment, i.e. according to the intention to treat principle, and will base evaluation of statistical significance on a two-sided test with level 0.05. The estimated relative hazard in the K-877 group compared to the placebo group with an accompanying 95% confidence interval will quantify the treatment effect. If this relative hazard is less than 1, then 100*(1-estimated relative hazard) will be defined as the percent reduction in hazard associated with K-877 treatment. Rates of occurrence of the primary endpoint will be defined as the total number of subjects who have this event in a treatment group per 100 person-years of follow-up. Estimates of the probability of the primary

```
Kowa Research Institute, Inc.
Statistical Analysis Plan – Protocol K-877-302 (PROMINENT)
```

endpoint by time after randomization within treatment groups will be based on the method of Kaplan and Meier.

Analysis will be implemented using the SAS® procedure PHREG as follows:

```
PROC PHREG DATA = ...;

CLASS TREATMENT (ref='2');

MODEL AVAL*CNSR(1) = TREATMENT;

STRATA SEX CVD STATIN;

HAZARDRATIO TREATMENT / ALPHA=0.05;

RUN;

where AVAL = time to event

TREATMENT = Randomized treatment group (pemafibrate and placebo)

CNSR = Censoring variable - 0 = Event, 1 = Censored

SEX = sex

CVD = prior history of CVD

STATIN = statin use at baseline
```

Additional analyses will separately evaluate whether the relative effects of K-877 versus placebo is uniform over the follow-up period. These evaluations will be based on the tests for significant interactions between study time and treatments proposed by Cox as well as consideration of trends in scaled Schoenfeld residuals in the proportional hazards model. Specifically, residuals will be plotted and a significant rank correlation of residuals with time will be indicative of a changing effect. In the presence of significant correlation, separate effects by time period will be reported. However, even with a significant correlation of residuals with time, the best overall estimate of the effect of treatment will be the estimate obtained from the proportional hazards model without the interaction.

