11. ASSESSMENT OF EFFICACY

11.1. Monitoring for the Occurrence of Cardiovascular Events

Monitoring for the occurrence of CV events will occur through querying the participant at each study visit. Documentation in the form of medical records will be collected and used in endpoint adjudication. Formal definitions for the individual components of the primary endpoint, all-cause mortality, and hospitalization for HF are provided below:

Endpoint Definitions and Documentation

Clinical endpoints defined as primary or secondary efficacy parameters will be assessed beginning with the day of randomization. Although excluded from the efficacy assessments, clinical endpoint events occurring between the Screening/Enrollment Visit (ie, the time of informed consent) and randomization will also be identified. All potential clinical endpoint events are collected for all randomized participants through study completion/CSED Visit whether or not the participant is currently receiving study drug. A complete description of the endpoints, data to be collected, and methodology for adjudication of both primary and secondary endpoints will be detailed in a Clinical Endpoint Committee (CEC) Charter. Primary and secondary endpoint definitions are included below. (Note: effective from global protocol amendment 2, "Hospitalization for Unstable Angina Requiring Unplanned Revascularization" will be part of the 4-component secondary efficacy endpoint.)

It is important to note, that the study medication will not be interrupted for reported or confirmed primary or secondary endpoints.

Definition of Myocardial Infarction

Acute MI: The definition of MI used in PROMINENT is consistent with the Third Universal Definition of MI.⁶¹ The term MI should be used when there is evidence of myocardial necrosis in a clinical setting consistent with acute myocardial ischemia. Under these conditions, any 1 of the following meets the diagnosis for MI:

Spontaneous MI: Detection of a rise and/or fall in cardiac biomarker values (preferably cardiac troponin [cTn]), with at least 1 value above the 99th percentile of the upper reference limit (URL) and with at least 1 of the following:

- Symptoms of ischemia
- New or presumed new significant ST-segment-T wave (ST-T) changes or new left bundle branch block (LBBB)
- Development of pathological Q waves in the electrocardiogram (ECG)*
- Imaging evidence of new loss of viable myocardium or new regional wall motion abnormality

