Rates of occurrence of the primary endpoint will be defined as the total number of participants who have this event in a treatment group per 100 person-years of follow-up, counting all time from randomization until the first of the event, death, end of trial, or withdrawal of consent, whichever comes first. Estimates of the probability of the primary endpoint by time after randomization within treatment groups will be based on the method of Kaplan and Meier. 66 We will also use the proportional hazards model to control for baseline factors that might influence the rate of the primary endpoint (eg, age, race, sex, baseline comorbidities, and concomitant medications), as control for these variables may yield more efficient estimates of relative treatment effects. 67 If Kaplan-Meier plots of event-free survival by study time, or related plots of log(-log)(survival), indicate violations of the proportional hazards assumption, or a formal test of trend in the scaled Schoenfeld residuals indicates such a violation, then weighted log-rank tests will be used according to strategies described by Pecková and Fleming.⁶⁸ However, even in the presence of an apparent violation of the proportional hazards assumption, the primary analysis described above gives a valid (although perhaps not optimal) test of the main study hypothesis and will remain the primary analytic strategy, with these weighted log-rank tests serving as sensitivity analyses.

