participants who received at least 1 dose of study treatment. Participants will be analyzed according to their randomized treatment group, regardless of whether they adhere to their assigned treatment. Statistical significance will be based on a 2-sided test with level 0.05. The estimated relative hazard in the pemafibrate group compared to the placebo group with an accompanying 95% confidence interval (CI) will quantify the treatment effect. If this relative hazard is less than 1, then 100*(1-estimated relative hazard) will be defined as the percent reduction in hazard associated with pemafibrate treatment. Rates of occurrence of the primary endpoint will be defined as the total number of participants who have this event in a treatment group per 100 person-years of follow-up, counting all time from randomization until the event, death, end of trial, or withdrawal of consent, whichever comes first. Estimates of the probability of the primary endpoint by time after randomization within treatment groups will be based on the method of Kaplan and Meier. We will also use the proportional hazards model to control for baseline factors that might influence the rate of the primary endpoint (eg. age, race, sex, baseline comorbidities, and concomitant medications), as control for these variables may yield more efficient estimates of relative treatment effects. If Kaplan-Meier (KM) plots of event-free survival by study time, or related plots of log (-log) (survival), indicate violations of the proportional hazards assumption, or a formal test of trend in the scaled Schoenfeld residuals indicates such a violation, then weighted log-rank tests will be used according to strategies described by Pecková and Fleming¹¹. However, even in the presence of an apparent violation of the proportional hazards assumption, the primary analysis described above gives a valid (although perhaps not optimal) test of the main study hypothesis and will remain the primary analytic strategy, with these weighted log-rank tests serving as sensitivity analyses.

Secondary Analyses:

Secondary clinical endpoint analyses will follow the same outline as the primary analysis for time to event data. Secondary lipid efficacy endpoints will use analysis of covariance with adjustment for baseline measurements and imputation of missing values.

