3.2. Study Endpoints

3.2.1. Primary Endpoint

The primary efficacy endpoint is the time from randomization to the first occurrence of any component of the clinical composite endpoint of:

- Nonfatal MI
- Nonfatal ischemic stroke
- Coronary revascularization
- Cardiovascular death

All events will be adjudicated following processes outlined in the Clinical Endpoint Committee (CEC) charter.

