8.4.2. Sensitivity Analyses of the Primary Efficacy Results

Two main types of sensitivity analyses will be done for the primary efficacy results. One sensitivity analysis will be to repeat the primary analysis on the Per-Protocol population. The other includes post-randomization changes in other lipid-lowering therapies.

Sensitivity of the results to post-randomization changes in other lipid-lowering therapies will be assessed using a combination of strategies. As noted in the subgroup analyses, the results will be stratified by baseline statin use. Additionally, an inverse probability treatment weighted approach as developed by Robins and Hernan⁸ will be used to account for time varying changes in lipid-lowering therapy and to obtain an adjusted treatment effect estimate.

Additional analysis to clearly explore the efficacy over time will be performed as follows:

Primary endpoint as well as every component of the primary endpoint will be summarized by treatment and by within year from randomization (first year from randomization, second year from randomization, third year from randomization, fourth year from randomization, and greater than 4 years from randomization).

Secondary endpoints will also by summarized similar to the primary endpoint by within year from randomization.

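### SAP 8.4.1 defines the primary endpoint as time from randomization but computes it from the date of first dose, with no rule for events that precede dosing

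*SAP*

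**What the plan says.** The SAP names randomization as the time origin in several places.

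- SAP 3.2.1: "The primary efficacy endpoint is the time from randomization to the first occurrence of any" component of the composite.
- SAP 8.4.1, opening sentence: "The primary endpoint of the trial is the time from randomization to the first occurrence of any component of the clinical composite endpoint".
- SAP 8.4.1, event probabilities: estimates of the primary "endpoint by time after randomization within treatment groups will be based on the method of Kaplan and Meier".
- SAP Technical Summary Report, rate definition: "counting all time from randomization until the event, death, end of trial, or withdrawal of consent, whichever comes first".
- SAP 7.1 counts days in trial from the date of randomization, plus 1.

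Protocol 14.4 agrees: "counting all time from randomization until the first of the event, death, end of trial, or withdrawal of consent". Protocol 11.1 adds that "Clinical endpoints defined as primary or secondary efficacy parameters will be assessed beginning with the day of randomization".

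The derivation rule in SAP 8.4.1 differs: "The time to event/censoring in days will be derived as (Date of First Occurrence of Event/Censoring – Date of First Dose) +1".

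Protocol 9.1 and 9.5 start dosing on the day after the Randomization Visit (Visit 2). SAP 6.4.3 defines the ITT population as randomized subjects who took at least one dose.

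**The concern.** The formula for the primary variable contradicts the definition given earlier in the same section. The two dates differ by design, because dosing starts the day after randomization.

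An event between randomization and first dose is a valid endpoint under protocol 11.1. A participant with a nonfatal event in that interval who then starts drug is in the ITT population, and the protocol (6.1 and 11.1) wants study drug continued after an endpoint. Such a record therefore has to be analysed, yet the formula gives it a time of zero or less. The SAP does not say whether to keep, shift or exclude it, and the model code in 8.4.1 gives no instruction. For the primary variable, that choice should not be left to the programmer.

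**Working it through.** **1. The formula.** Let an event occur *k* days after randomization and first dose be taken *g* days after randomization. SAP 8.4.1 gives *k* − *g* + 1. A randomization origin with the same +1 gives *k* + 1, whatever *g* is.

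| Gap *g* | *k* = 0 | *k* = 1 | *k* = 2 | *k* = 3 |
|---|---|---|---|---|
| 0 days | 1 | 2 | 3 | 4 |
| 1 day (planned) | 0 | 1 | 2 | 3 |
| 2 days | −1 | 0 | 1 | 2 |
| 3 days | −2 | −1 | 0 | 1 |
| Randomization origin, any *g* | 1 | 2 | 3 | 4 |

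At the planned gap the result equals *k*, the elapsed days since randomization. Values of zero or below arise only when *k* < *g*, that is, for events before first dose.

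**2. Do other SAP rules settle such a record?**
- SAP 6.6.2 defines study day and is not cited in 8.4.1. For a randomization-day event at *g* = 1 it gives 0 − 1 = −1, where 8.4.1 gives 0.
- SAP 6.7.1 covers only partially missing endpoint dates. Its start date is that of the Overall Study Period, which SAP 6.4.5 sets at first treatment.
- SAP 6.4.5 does not say that earlier events are excluded.

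**3. The plan's event target.** Inputs from protocol 14.2: hazard ratio 0.834, two-sided alpha 0.05, power 90%. Schoenfeld's formula, 4(1.960 + 1.282)² / (ln 0.834)², gives 1,276 events, and Freedman's gives 1,283. The protocol states 1,279. Then 1,279 × 1.019 = 1,303.3, rounded up to 1,304. The target is reproduced.

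**4. How many events could be affected?** Inputs: 10,000 participants and placebo rates of 3.5, 4.0 or 4.5 per 100 person-years (protocol 14.2). Nobody has taken drug before first dose, so the placebo rate applies to both arms. Events per day of mean gap = 10,000 × rate / 100 / 365.25:

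| Placebo rate | Events per day of gap | Share of 1,304 |
|---|---|---|
| 3.5 | 350 / 365.25 = 0.96 | 0.073% |
| 4.0 | 400 / 365.25 = 1.10 | 0.084% |
| 4.5 | 450 / 365.25 = 1.23 | 0.094% |

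These are upper bounds, because anyone who dies before dosing, or never starts drug, is outside the ITT population.

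**5. What if all such records were lost?** Actual gaps are not given, so the mean gap is an assumption. Power is Φ(√D × |ln 0.834| / 2 − 1.960), where D is the number of events. With D = 1,304 it is 0.9062.

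| Assumed mean gap | Events lost (rates 3.5 to 4.5) | Power |
|---|---|---|
| 1 day | 0.96 to 1.23 | 0.9060 to 0.9059 |
| 7 days | 6.71 to 8.62 | 0.9047 to 0.9043 |
| 14 days | 13.42 to 17.25 | 0.9033 to 0.9025 |

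The documents do not say that such records would be lost, so this is a worst case.

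**The case against.** The strongest reply is that on the protocol's schedule the formula already measures time from randomization: with a one-day gap the +1 cancels the gap. Time 0 for a randomization-day event is then its true elapsed time. A shift common to all participants also leaves the order of event times unchanged, and therefore the Cox hazard ratio and likelihood ratio test. Only gaps that vary between participants could matter, and in a double-blind trial there is no evident reason for them to differ by arm. All of this stands.

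Two further points stand in part. SAP 8.4.1 invokes the intention-to-treat principle and SAP 6.7.1 favours including more events. Both argue against silently dropping a record, but neither is a rule for a fully dated event before first dose. Also, not every mention of randomization contradicts the formula. The summaries "summarized by treatment and by within year from randomization" in SAP 8.4.2 can be built from randomization dates whatever the Cox time variable is, and protocol 11.1 says when endpoint assessment begins, not how time is computed.

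The reply does not remove the mismatch within 8.4.1. Drug is self-administered by outpatients, so some may start later than planned, and for them the two origins do diverge.

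**Conclusion.** The derivation in SAP 8.4.1 is wrong as written: it contradicts the endpoint definition in its own section, SAP 3.2.1, the rate definition and protocol 14.4. It also leaves events before first dose without a stated handling. The expected effect is very small, at most about one event per day of mean gap among 1,304. That bound rests on the protocol's placebo rates applied to both arms and on assumed gaps.

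A reader might infer that primary events are generally mis-timed, that early events will be lost, or that the hazard ratio is biased. The documents support none of these. At the planned gap the times are correct elapsed days, nothing says that records at time 0 or below are removed, and there is no evidence of gaps differing by arm. This is a minor correction of the specification.

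**What to change.** In the SAP 8.4.1 formula, replace the date of first dose with the date of randomization and keep the +1. Every event on or after randomization then has a time of at least 1, and no separate rule is needed. The interim and secondary time-to-event analyses follow without further wording: SAP 5.2 ties interim methodology to the final analysis, and SAP 8.5 has those secondary analyses mirror the primary one.

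An optional conforming edit is to use the randomization date as the start date for imputing endpoint-event dates in SAP 6.7.1. Because 6.7.2 borrows the 6.7.1 approach, the edit should say that it applies to endpoint events only. The Overall Study Period (6.4.5) and the medication and adverse-event date conventions (6.7.2, 6.7.3) stay as they are.

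The cost is one term in one sentence, plus the optional edit. The randomization date is already used in SAP 7.1, so no new data or protocol change is needed, and the event target of 1,304 is unaffected. If the SAP can no longer be amended, SAP section 2 provides for noting the deviation in the clinical study report.

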8.4.2. Sensitivity Analyses of the Primary Efficacy Results

Two main types of sensitivity analyses will be done for the primary efficacy results. One sensitivity analysis will be to repeat the primary analysis on the Per-Protocol population. The other includes post-randomization changes in other lipid-lowering therapies.

Sensitivity of the results to post-randomization changes in other lipid-lowering therapies will be assessed using a combination of strategies. As noted in the subgroup analyses, the results will be stratified by baseline statin use. Additionally, an inverse probability treatment weighted approach as developed by Robins and Hernan⁸ will be used to account for time varying changes in lipid-lowering therapy and to obtain an adjusted treatment effect estimate.

Additional analysis to clearly explore the efficacy over time will be performed as follows:

Primary endpoint as well as every component of the primary endpoint will be summarized by treatment and by within year from randomization (first year from randomization, second year from randomization, third year from randomization, fourth year from randomization, and greater than 4 years from randomization).

Secondary endpoints will also by summarized similar to the primary endpoint by within year from randomization.

8.5. Analysis of the Secondary and Tertiary Efficacy Endpoints

In addition to the primary comparisons of K-877 treatment with placebo, prespecified secondary efficacy endpoints will also be compared between treatment groups.

A sequential gate-keeping procedure will be used for the secondary endpoint testing to control for the overall type I error at the 0.05 significance level. The primary endpoint will be tested first at the 0.05 significance level, secondary endpoints will only be evaluated if primary endpoint is positive. The total secondary endpoint alpha of 0.05 will be allocated between the two secondary endpoints groups. Group A will be allocated an alpha of 0.049 and Group B will be allocated 0.001. Within each secondary endpoint group, a hierarchical testing structure will be followed, if the testing is found to be statistically significant then proceed to the next endpoint testing at the significance level of the group, otherwise stop testing. The hierarchical testing will be based on the order of endpoints defined in Sections 3.2.2.1 and 3.2.2.2.

The order of Group A secondary endpoints is as follows:

- 1. The 4-component composite endpoint of non-fatal MI, non-fatal ischemic stroke, hospitalization for unstable angina requiring unplanned coronary revascularization or cardiovascular death
- 2. Any component of the 3-component composite endpoint of non-fatal MI, non-fatal ischemic stroke, or cardiovascular death
- 3. Any component of the primary endpoint or hospitalization HF
- 4. Any component of the primary endpoint or all-cause mortality
- 5. Any new or worsening PAD
- 6. Individual endpoints and an analysis of total events (first and all recurrent non-fatal MI, nonfatal ischemic stroke, coronary revascularization, or cardiovascular death)
- 7. Heterogeneity of effect by PPAR-α genetic polymorphisms, in particular but not limited to rs6008845.

Analysis of time to event Group A secondary endpoints 1-5 and individual endpoints analysis (first part of endpoint 6) will mirror the primary analysis. Specifically, analyses of these secondary endpoints will use a likelihood ratio test based on a proportional hazards model stratified on sex, prior history of CVD, and statin use at baseline to test the null hypothesis of no association between assignment to active K-877 and the rate of a specific secondary endpoint.

The total events analysis (second part of endpoint 6) will use negative binomial regression, with outcome being the total number of such events, a log link function, and a subject's total follow-up time as an offset. The independent variable will be randomized treatment assignment, and the

```
Kowa Research Institute, Inc.
Statistical Analysis Plan – Protocol K-877-302 (PROMINENT)
```

model will consider the following variables as fixed effects: sex, prior history of CVD, and statin use at baseline.

The analysis of heterogeneity of treatment effect by PPAR- α genetic polymorphisms will use a Cox proportional hazards model including two stratification variables: sex and prior history of CVD. This is due to both the low level of statin intolerance at baseline and concern that some of the genetic subgroups may be sparse.

In addition to the separate analyses of each component of the primary endpoint, possible heterogeneity in their effects across components will be evaluated. Analyses will use methods of competing risks survival analysis and compare the relative effects of randomized treatments on the different components of the composite outcome^{4, 5}. The approach of Fine and Gray provides a readily accessible implementation of a classical approach to competing risk analysis developed by Kalbfleisch and Prentice⁶.

In addition to the individual components of the composite primary endpoint, other CVD endpoints will be evaluated for treatment effect, including time to all-cause mortality, time to first MI, time to first stroke, time to first ischemic stroke, and time to first hemorrhagic stroke. Analyses will consider both fatal and non-fatal events where appropriate.

Secondary Group B lipid efficacy endpoints will be analyzed using analysis of covariance (ANCOVA) with a retrieved dropout based pattern mixture model. Subjects with missing data will be imputed using the distribution of retrieved dropouts for each arm, where retrieved dropouts are defined as participants who are no longer taking study drug but have agreed to continue to be followed. Imputed data will be analyzed using an ANCOVA model with baseline measurement as a covariate and the treatment arm and randomization strata as fixed effects.

Analysis using an ANCOVA model will be implemented using the SAS® procedure MIXED as follows:

```
PROC MIXED DATA = ...;

CLASS TREATMENT SEX CVD STATIN;

MODEL PCHG = BASELINE TREATMENT SEX CVD STATIN;

LSMEANS TREATMENT / DIFF CL;

RUN;

where PCHG = percent change from baseline

TREATMENT = Randomized treatment group (pemafibrate and placebo)

BASELINE = baseline value

SEX = sex

CVD = prior history of CVD

STATIN = statin use at baseline
```

The time to event microvascular tertiary endpoints will be analyzed as outlined for the primary analysis. The other tertiary endpoints will be analyzed using MMRM method. Each model will include the endpoint result change from baseline at each study visit as the response variable and

```
Kowa Research Institute, Inc.
Statistical Analysis Plan – Protocol K-877-302 (PROMINENT)
```

study visit, randomization strata, baseline endpoint result, baseline result-by-study visit interaction, treatment, and treatment-by-study visit interaction.

Analysis using MMRM method will be implemented using the SAS® procedure MIXED as follows:

```
PROC MIXED DATA = ...;

CLASS VISIT SEX CVD STATIN TREATMENT SUBJID;

MODEL CHG = VISIT SEX CVD STATIN BASELINE BASELINE*VISIT

TREATMENT TREATMENT*VISIT / DDFM=KR;

REPEATED VISIT / SUBJECT = SUBJID TYPE=UN;

LSMEANS TREATMENT*VISIT / DIFF CL;

RUN;

where CHG = change from baseline at each study visit

TREATMENT = randomized treatment group (pemafibrate and placebo)

BASELINE = baseline value

SEX = sex

CVD = prior history of CVD

STATIN = statin use at baseline

VISIT = study visit

SUBJID = subject ID
```

If the MMRM model using an unstructured covariance matrix fails to converge with the default Newton-Raphson algorithm, the Fisher scoring algorithm will be used to provide initial values of the covariance parameters. In the rare event that none of the above methods yields convergence, a structured covariance, such as heterogeneous Toeplitz and Toeplitz structures, will be used to model the correlation among repeated measurements. In this case, the empirical option will be used because the sandwich variance-covariance estimator is asymptotically consistent.

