8.3. Subgroup Analyses

Subgroup analyses will be conducted for the primary endpoint and each individual component as well as other endpoints as needed. Where applicable, each subgroup will be analyzed using a Cox proportional hazard model including treatment and the two stratification variables: sex and prior history of CVD. Due to the low level of statin intolerance at baseline, primary subgroup analyses will not stratify on statin use at baseline. The descriptive summaries and the two sided 95% CIs for the hazard ratio will be provided. Likelihood tests for treatment by subgroup interaction comparing models with and without interaction terms between treatment and categories will also be assessed. While a formal test for heterogeneity of treatment effect by country or center has not been prespecified, center level deviations will be monitored across multiple operational quality measures such as rate of discontinuation of study drug to ensure there are no systematic differences introduced during the study.

The subgroups may be based on characteristics including but not limited to the list below.

Variable	Categories			
Baseline Subgroups				
Sex	Men, Women			
Established Cardiovascular Disease	Yes, No			
Statin Use	Defined as those who are taking no statin at baseline or are statin intolerant compared to all others.			
Region	Africa,			
	Asia (comprising Japan, Israel and India),			
	Eastern Europe,			
	Latin America,			
	US/Canada,			
	Western Europe			
Age	<65,			
	>=65			
BMI (kg/m²)	<30,			
	30-34,			
	>=35			
Race	Asian,			
	Black or African American,			
	White,			
	Other (including, Other, Multiracial and Not Reported)			
Ethnicity	Hispanic or Latino,			
	Not Hispanic or Latino,			
	Unknown/Not Reported			
Duration of Diabetes	<10 years,			

	>=10 years			
Hypertension	Yes, No			
HDL	Above/below median at baseline (screening value)			
LDL	Above/below median at baseline (screening value)			
Fasting TG	Above/below median at baseline (screening value)			
Non-Fasting TG	Above/below median at baseline (randomization value)			
Non-HDL Cholesterol	Above/below median at baseline (screening value)			
АроВ	Above/below median at baseline (screening value)			
Non-fasting Remnant Cholesterol	Above/below median at baseline (randomization visit)			
HbA1c	Above/below median at baseline (screening value)			
hsCRP	Above/below median at baseline (screening value)			
CYP3A4 or CYP2C8 Inhibitor Use	Yes, No			
Ezetimibe Use	Yes, No			

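### SAP 8.5 puts several tests into item 6, and an open number into item 7, of the alpha-controlled Group A order without a rule for passing them, so the stated error control is not guaranteed at those two items (minor)

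*SAP*

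**What the plan says.** SAP 8.5 introduces a sequential gate-keeping procedure "to control for the overall type I error at the 0.05 significance level". The primary endpoint comes first at 0.05. If it is positive, Group A receives 0.049 and Group B 0.001. Within a group the rule is: "if the testing is found to be statistically significant then proceed to the next endpoint testing at the significance level of the group"; otherwise testing stops. On the sequence it says: "The hierarchical testing will be based on the order of endpoints defined in Sections 3.2.2.1 and 3.2.2.2".

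SAP 3.2.2.1 numbers seven Group A items, and SAP 8.5 repeats all seven as the order. Items 1 to 4 are composites and item 5 is "Any new or worsening PAD". Item 6 is "Individual endpoints and an analysis of total events (first and all recurrent non-fatal MI, nonfatal ischemic stroke, coronary revascularization, or cardiovascular death". Item 7 is heterogeneity of effect by PPAR-α "genetic polymorphisms, in particular but not limited to rs6008845".

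SAP 8.5 itself treats item 6 as two parts. The individual endpoints follow the primary Cox analysis, with a likelihood ratio test each, and "The total events analysis (second part of endpoint 6) will use negative binomial regression".

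Protocol 14.5 allocates the same 0.049 and 0.001, but bases the hierarchy on a numbered list that stops at endpoint 5 (PAD). Individual endpoints and total events then appear as work beyond that list, and the genetic question as a prespecified secondary analysis; neither carries a number.

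**The concern.** A fixed-sequence procedure spends the full group alpha at every step, and this is valid because each step is one hypothesis. Item 6 is several, and item 7 may be. The step rule speaks of the testing being significant, but does not say whether one success or all successes pass the item. It also gives no order or alpha split inside it. Item 7 depends on item 6, so even permission to test genotype heterogeneity rests on an undefined event.

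What is at stake is a labelling claim late in the sequence. If everything through PAD succeeds, a component with no true effect and a nominal p-value below 0.049 could be reported as alpha-controlled under the SAP. Under Protocol 14.5 the same result would be supportive only.

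**Working it through.** **1. The plan's own figure.** Group A 0.049 + Group B 0.001 = 0.05, as stated. This holds when each step is a single test at the group level. A false claim in Group A then requires rejecting the first true null in the order, which has probability at most 0.049.

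**2. Number of tests per step.**
- Items 1 to 5: one each.
- Item 6: the primary endpoint has four components (SAP 8.4.1), so four Cox tests plus one total-events test = 5, if individual endpoints means those four.
- Item 7: for rs6008845 alone it could be one test. SAP 8.3 defines three genotype groups and states: "Likelihood tests for treatment by subgroup interaction comparing models with and without interaction terms between treatment and categories will also be assessed". The number of further polymorphisms is not given, so item 7 is not quantified here.

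**3. The two documents side by side.**

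| Analysis | Protocol 14.5 | SAP 8.5 |
|---|---|---|
| Endpoints 1 to 5 | numbered order | numbered order, same sequence |
| Individual endpoints, total events | after the list, unnumbered | item 6 |
| Genotype heterogeneity | after the list, unnumbered | item 7 |

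**4. Ceiling at item 6.** Suppose every earlier gate is certain to be passed, any single success counts, and the k true-null components are independent. The error is 1 − (1 − 0.049)^k:
- k = 2: 1 − 0.951² = 0.0956, or 9.6%
- k = 3: 1 − 0.951³ = 0.1399, or 14.0%

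The case of four null components is not a worse one. The primary composite would then be null too, and item 6 could be reached only after a false-positive primary result.

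**5. Effect of the earlier gates.**
- If PAD is truly null, a false claim at item 6 requires PAD to have been falsely rejected first. So P(error at item 6) ≤ P(PAD rejected) ≤ 0.049, whatever the correlations.
- If all components share HR 0.834, no component is null and no false component claim is possible.
- For uneven effects, a simulation used 600,000 runs per scenario and 1,304 events, with component statistics normal around ln(HR) × √events / 2. The primary and 3-component gates were applied; steps 1, 3, 4 and 5 were taken as passed. Any null component with two-sided p < 0.049 counted as a false claim. Assumed event shares (MI/stroke/revascularization/CV death) were 25/12/43/20, 20/10/55/15 and 30/15/30/25, with pairwise correlation 0 or 0.3. The effect was placed on MI alone, MI and CV death, or MI and revascularization. At HR 0.834 on the affected components, no scenario exceeded 4.9%.
- At HR 0.70 or stronger on some components and none on others, some scenarios did exceed 4.9%. Their size is not relied on, for reasons given under the objection.

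**The case against.** **The conflict between the documents is not clean.** This stands in part. Steps 1 to 5 are identical in both. Protocol 5.2.1 lists the individual endpoints, total events and genetic analysis under its Group A heading, which favours the SAP's placement. Conversely, the Secondary Analyses text in the SAP's Technical Summary Report, and Appendix 1 (Amendment 2, changes 7 and 8), describe them as additional secondary analyses. A reader might infer two flatly opposed plans; the documents support only an inconsistency in numbering and wording. Still, only Protocol 14.5 and SAP 8.5 set a testing order, and those two orders end at different places.

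**An all-must-pass reading keeps 0.049.** Correct. It is the reason for saying that control is not guaranteed rather than that it is lost. The SAP states neither reading.

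**The size is small and the simulation fragile.** This largely stands. The documents give no component event mix, PAD event count or correlation. At correlation 0.3 the simulated primary power at a uniform HR 0.834 is only 67–69%, against the planned 90%; at correlation 0 it is about 90.6%. Results at stronger effects also depend on whether a null component significant in the harm direction counts as a false claim. They therefore show that an excess is possible, not how large it is. Strong effects are not outside the trial's rationale: HR 0.70 is close to the 29% pooled reduction cited in Protocol 4.4.

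**Item 7 may be a single test.** Also fair. The open point there is the unspecified list of polymorphisms and the undefined gate before it.

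**Conclusion.** The stated type I error control is not guaranteed at items 6 and 7 as written, because the SAP gives no within-item order, alpha split or pass rule. The ceilings of 9.6% and 14.0% rest on independence, every gate being passed, and any single success counting. With the gates in place, an excess over 4.9% needs strong and uneven component effects together with a real PAD effect.

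A reader might infer that the trial's overall conclusion, or the family-wise error in general, is inflated to these ceilings. The documents do not support that. The primary test and Group A steps 1 to 5 precede the affected items, and Group B has its own 0.001. Severity is minor: it affects how two late, supportive analyses may be described.

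**What to change.** In SAP 8.5 and 3.2.2.1, end the alpha-controlled Group A order at endpoint 5, as Protocol 14.5 does. Report individual endpoints, total events and genotype heterogeneity outside it, with nominal confidence intervals and no significance claims. Group A is then five single-hypothesis steps with error at most 0.049, and 0.049 + 0.001 = 0.05 holds.

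If the sponsor wants confirmatory claims on components, state a within-item rule instead. One example is total events as step 6, then Holm at 0.049 over the four components, with genotype kept outside the order. The smallest component p-value must then be at or below 0.049 / 4 = 0.01225 before any component can be claimed, and the SAP should say how this extends the order in Protocol 14.5.

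The preferred change is SAP wording only. No analysis is dropped and nothing in the protocol's numbered order is lost; the cost is that these three sets of results carry no alpha-controlled claim.
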